4.1.3 Crude Cumulative Incidence

Crude estimates of the cumulative incidence, defined as the number of incident outcomes occurring up to a time point out of the number of IUD insertions, will be estimated using the Kaplan-Meier method.

4.1.4 Crude Hazard Ratios

Crude hazard ratios will be estimated using Cox regression models. These crude hazard ratios will be calculated for each outcome without adjustment for covariates. All crude hazard ratios will be reported as point estimates with 95% CIs.

The proportional hazards assumption between each exposure-outcome pairing will be assessed using visual examination of hazard functions, log-log survival curves, and goodness-of-fit testing using Schoenfeld residuals (Kleinbaum and Klein, 2012). Parallel hazard function and log-log survival curves for exposure groups (i.e., the vertical distance between exposure groups is constant) would indicate that the assumption of proportional hazards is met. The hazard function and log-log plot will be generated using the PLOTS=(H LLS) option in the PROC LIFETEST procedure in SAS. The goodness-of-fit global correlation test based on Schoenfeld residuals will be conducted using the ZPH(GLOBAL) option in the PROC PHREG procedure in SAS. A test with $P < 0.05$ will indicate that the proportional hazards assumption does not hold. If both visual examination and the global correlation test suggest nonproportional hazards, the time-dependent exposure covariate will be included in crude and adjusted hazard ratio models by fitting interaction terms with continuous or categorical time (Paul, 1995). The form of the interaction terms will be determined after reviewing the plots of hazard functions and log-log survival curves. An example SAS program code follows, where *brstime* is the time-dependent exposure covariate created with the programming statement in the PHREG procedure as an exposure-by-time interaction:

```
PROC PHREG DATA=start;
  CLASS brstfeed;
  MODEL personyr * outcome (0) = brstfeed brstime / TIES=EFRON;
  brstime = brstfeed * (personyr > 0.5); /* use 0.5 as an example*/
RUN;
```

For any models including time-dependent exposure covariates, separate hazard ratios will be reported for estimates of the effect of the exposure over time.

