9.7.1.2 Crude incidence rates and crude cumulative incidence

9.7.1.2.1 Crude incidence rates

While the main study analyses will account for the anticipated underlying change in risk of outcomes across the time women are exposed to inserted IUDs, constant incidence rates will also be calculated across the person-time women contribute to the study. Following characterization of variables, person-time at risk and crude incidence rates of outcomes will be calculated. Crude incidence rates will be assessed rather than incidence proportions, since patients will contribute variable time at risk to the study. Crude incidence rates will be calculated for all study cohorts and within levels of exposure variables.

Crude incidence rates will be calculated as the number of outcomes occurring during the person-time at risk divided by the total person-time at risk (in person-years). Crude incidence rates will be reported as point estimates (number of cases per 1,000 person-years) and 95% CIs.

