9.7.1.3 Crude and adjusted hazard ratios

9.7.1.3.1 Crude hazard ratios

In binary comparisons, crude hazard ratios will be estimated for the exposed group (e.g., breastfeeding at the time of IUD insertion) relative to the referent group (e.g., not breastfeeding at the time of IUD insertion) using Cox regression models. In categorical comparisons, crude hazard ratios will be estimated for each exposure group (e.g., IUD insertion ≤ 6 weeks postpartum) relative to the referent group (IUD insertion > 52 weeks postpartum) using Cox regression models. These crude hazard ratios will be calculated for each outcome without adjustment for covariates. All crude hazard ratios will be reported as point estimates with 95% CIs.

The proportional hazards assumption between each exposure and outcome pairing will be assessed using visual examination of hazard functions, log-log survival curves, and goodness-of-fit testing

using Schoenfeld residuals (Kleinbaum and Klein, 2012). For violations of the proportional hazards assumption, time-dependent exposure covariates will be included in crude and adjusted hazard ratio models by fitting interaction terms with continuous or categorical time. Additional details are included in the statistical analysis plan.

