4.1.6 Adjusted Hazard Ratios

The adjusted hazard ratios and 95% CIs will be estimated using weighted Cox regression models. Hazard ratios will be adjusted for possible confounding effects using overlap weighting (Section 4.1.5). This will be conducted in SAS using PROC PHREG with the WEIGHT statement. Normalized weights will be used for the weighted Cox models. The normalized weights add up to the sample size, so that the estimated covariance matrix of the parameter estimators is invariant to the scale of the weights. To account for the fact that the weights are estimated, a robust, sandwich-type variance estimator will be used to calculate 95% CIs. This will be conducted by using the COVSANDWICH option in the PROC PHREG procedure in SAS. Adjusted hazard ratios will be reported as point estimates with 95% CIs.

Time-dependent exposure covariates will be included if violation of the proportional hazards assumption is identified in the unweighted Cox model (described in Section 4.1.4.).

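### SAP 4.1.4 takes a constant vertical distance as the sign of proportional hazards on the hazard plot as well as on the log-log plot; on the hazard plot that is the additive-hazards condition

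*SAP*

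**What the plan says.** SAP section 4.1.4 sets out three diagnostics for each exposure-outcome pairing: a hazard-function plot, a log-log survival plot and a test on Schoenfeld residuals.

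- **Plots.** "The hazard function and log-log plot will be generated using the PLOTS=(H LLS) option" of the SAS life-table procedure. No log scale is named for the hazard plot.
- **Visual criterion.** One sentence covers both plots: "Parallel hazard function and log-log survival curves for exposure groups (i.e., the vertical distance between exposure groups is constant) would indicate" that the assumption is met.
- **Test.** "The goodness-of-fit global correlation test based on Schoenfeld residuals will be conducted using the ZPH(GLOBAL) option", with P < 0.05 read as a violation.
- **Decision rule.** "If both visual examination and the global correlation test suggest nonproportional hazards", an exposure-by-time term is added to the crude and adjusted models, and separate hazard ratios over time are reported. The form of that term is chosen after looking at the same two plots.
- **Carry-over.** SAP section 4.1.6 applies the decision to the overlap-weighted model: "Time-dependent exposure covariates will be included if violation of the proportional hazards assumption is identified in the unweighted Cox model".

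Protocol section 9.7.1.3.1 names the same three tools (the assumption "will be assessed using visual examination of hazard functions, log-log survival curves" and Schoenfeld residuals). It contains neither the constant-distance definition nor the requirement that plots and test agree. Protocol section 9.7.1.2.1 says the main analyses will account for "the anticipated underlying change in risk of outcomes across the time women are exposed to inserted IUDs".

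**The concern.** The proportional hazards model says that one group's hazard is a fixed multiple of the other's. On the log-log survival scale, a fixed multiple appears as a fixed vertical gap. On the natural hazard scale, it appears as a gap that widens and narrows with the baseline hazard. The SAP gives both plots the fixed-gap criterion, so it is right for one and wrong for the other.

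This matters because the plots are half of a prespecified rule. The rule decides whether each primary objective is reported as one hazard ratio or as hazard ratios that vary over follow-up. Because plots and test must agree before the model changes, the visual check is meant to stop a chance-significant test from changing the primary model. A visual criterion that a truly proportional effect cannot meet does not do that job. The SAP also does not say which plot prevails when they conflict, and it uses the hazard plot to shape any time interaction.

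**Working it through.** **1. The plan's own figure.** Protocol sections 4.8 and 9.5 give 60,000 insertions for objective 1, a risk of 1.3 per 1,000 at 1 year, a 60:40 allocation and two-sided alpha 0.05. Expected events are 60,000 × 0.0013 = 78. At a hazard ratio of 2.0, Schoenfeld's formula gives Φ(√(78 × 0.6 × 0.4) × ln 2 − 1.96) = Φ(4.327 × 0.693 − 1.96) = Φ(1.04) = 85%, as Protocol Table 4 states. Nothing below changes this.

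**2. Algebra.** Let h0 and h1 be the unexposed and exposed hazards.

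- Proportional hazards: h1(t) = r·h0(t). The natural-scale gap is (r − 1)·h0(t), which moves with h0. The log-log gap is ln r at all times.
- Constant natural-scale gap: h1(t) = h0(t) + c. The hazard ratio is 1 + c/h0(t), which changes whenever h0 does.
- Both together: r·h0 = h0 + c, so h0 = c/(r − 1), a constant, unless r = 1 and c = 0.

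So with a non-null effect and a changing baseline hazard, the two plots cannot both show parallel curves.

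**3. Size.** The documents give no hazard shape, so I assume Weibull baselines with cumulative hazard H0(t) = b·t^k (t in years) and show a range of shapes k. I scale to an overall 1-year risk of 1.3 per 1,000 at 60:40 and a 1-year cumulative hazard ratio of 2: b = 0.0013/(0.4 + 0.6 × 2) = 0.0008125. Then h0(t) = b·k·t^(k−1). The additive case uses a gap of 0.8125 per 1,000 person-years. Arrows run from month 1 to month 12; hazard gaps are per 1,000 person-years.

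| Shape k | Exact HR 2: hazard gap | Exact HR 2: log-log gap | Parallel hazards: HR(t) | Parallel hazards: log-log gap |
|---|---|---|---|---|
| 0.3 | 1.39 → 0.24 | 0.693 throughout | 1.59 → 4.33 | 0.16 → 0.69 |
| 0.5 | 1.41 → 0.41 | 0.693 throughout | 1.58 → 3.00 | 0.25 → 0.69 |
| 0.7 | 1.20 → 0.57 | 0.693 throughout | 1.68 → 2.43 | 0.39 → 0.69 |
| 1.0 | 0.81 → 0.81 | 0.693 throughout | 2.00 → 2.00 | 0.69 → 0.69 |

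Example, k = 0.5 at 1 month: h0 = 0.8125 × 0.5 × √12 = 1.41 per 1,000; with parallel hazards, HR = 1 + 0.8125/1.41 = 1.58. The two criteria coincide only in the last row, the constant hazard that the protocol does not expect.

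**4. What the rule then does.**

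- *Truth: proportional, non-null, changing baseline.* The log-log curves are parallel and the hazard curves are not. Read literally, the visual condition is not met, so the Schoenfeld test decides alone. I approximated that test by correlating exposure with event order at 78 events (3,000 simulations per shape). It rejected in 5.0% to 5.5% of runs. With a correct visual criterion, these chance rejections would normally be blocked.
- *Truth: parallel hazards, so a changing hazard ratio.* The hazard curves are parallel and the log-log curves are not. The sentence requires both, so the condition is again not met and the test again decides. It rejected in 42%, 19% and 9% of runs at shapes 0.3, 0.5 and 0.7. The misses reflect few events, not the wording. Follow-up beyond one year would bring more than 78 events.

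**The case against.** Most of the diagnostic is sound. Constant vertical distance is the correct criterion for log-log curves, and the residual test does not depend on the plots. An experienced analyst would probably rely on the log-log plot. The sentence says only what would indicate that the assumption is met; it does not say that non-parallel hazard curves prove a violation. That step is inference, though a natural one when two plots share one criterion. A 5% false-trigger rate is the nominal level of the stated test, and the protocol never required plots and test to agree. A false trigger yields hazard ratios by follow-up time, so it does not hide non-proportionality. Table Layouts 2.1 and 2.2 in SAP section 9.5 also print the test's P value beneath the primary results.

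All of this stands, and it limits the consequence. It does not make the criterion right for the hazard plot. If that plot were drawn on a log scale the wording would be correct, but the SAP does not say so.

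A reader might go further and infer that the whole rule rests on a wrong criterion, or that the SAP would call parallel hazard curves proportional and report one hazard ratio while the ratio changes several-fold. The text does not support this. It asks for parallel curves on both plots, and step 3 shows that parallel hazards under a changing baseline give visibly non-parallel log-log curves. That error arises only if an analyst lets the hazard plot override the log-log plot. The SAP does not direct this, but it does not exclude it either, because it names no order of precedence.

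**Conclusion.** Wrong as written, with a minor consequence. One of three diagnostics carries a criterion that belongs to additive hazards, and under the changing risk the protocol expects, a truly proportional non-null effect cannot satisfy the sentence. On a literal reading the visual safeguard drops out. The choice between one hazard ratio and time-varying ones then falls to the P < 0.05 test, at about 5% false triggers per pairing, and is carried into the weighted primary analysis. The error does not systematically favour keeping a single hazard ratio. The algebra needs no assumption beyond a natural-scale hazard plot. The gaps, ratios and rejection rates are illustrations that rest on the assumed Weibull shapes, the planned 1.3 per 1,000, 78 events and an approximate version of the test. Power, sample size and alpha are unaffected.

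**What to change.** Amend SAP section 4.1.4 in three places:

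1. Replace the criterion with wording such as: *Parallel log-log survival curves (constant vertical distance), or hazard curves with a constant ratio (parallel on a log scale), would indicate that the assumption is met.*
2. Add that the log-log plot is the deciding visual criterion if the plots disagree.
3. Keep the natural-scale hazard plot as descriptive. Where it helps to choose the form of a time interaction, say that it is read for the ratio between curves and not the distance.

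The cost is one or two sentences, with a log axis if a hazard plot is to serve as a criterion. No new data are needed. Protocol section 9.7.1.3.1 can stay as it is, since it does not contain the faulty definition.

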4.9 Data analysis

Descriptive analyses for all variables of interest will be presented overall and stratified by database.* For categorical variables, frequencies and percentages will be presented for each level. For continuous variables, the mean, standard deviation, minimum, maximum, median, and quartiles will be presented. For estimates, two-sided 95% confidence intervals will be calculated.

* Descriptive and comparative analyses for all variables of interest will be presented overall and stratified by database, with the exception of IUD type. The variable IUD type will be analyzed by database, but only each database holder and RTI-HS will have access to the database-specific information. Data shared with Bayer will only present IUD type aggregated over all data sources. Additionally, analyses for objectives 18 and 26 will be presented by database only if there are more than 20,000 subsequent IUD insertions for the research partner that can be included in the analysis.

Crude incidence rates and cumulative incidence of the outcomes will be estimated for each exposure group (i.e., postpartum IUD insertion time category, breastfeeding status at the time of IUD insertion, type of IUD [LNG vs. copper]).

Crude hazard ratios will be calculated for each outcome without adjustment for covariates within each database. Confounding adjustment will be performed via overlap weighting. Adjusted hazard ratios will be calculated accounting for the propensity score-based weighting approach.

Effect estimates across all data sources will be estimated and presented as the main study results. Effect estimates, except IUD type, will also be presented for each database.

Analyses of the adjusted hazard ratios for the two primary objectives (uterine perforation by breastfeeding status at IUD insertion and uterine perforation by postpartum timing of IUD insertion [in four categories]) combined across all data sources will include hypothesis testing using two-sided statistical tests with a significance level of 0.05 (as requested by the FDA) to test the hypothesis of no difference in the perforation risk between the exposed and referent groups. There will be no adjustment for multiplicity. Statistical tests will be conducted on the assumption that residual confounding can be neglected. However, the validity of this assumption cannot be assessed within the framework of this study.

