There were approximately 325,000 IUD insertions identified during the time frame of the validation/feasibility study (i.e., end date, 30 September 2015), and approximately 65% of those occurred after at least 12 months within the data source. In approximately 90% of IUD insertions, this was the first observed insertion for each woman. Approximately 30% of women were identified as having an IUD inserted within the first 52 weeks postpartum. Based on these results and assumptions—approximately three additional years of data more than the validation study and allowing for a loss of approximately 15% of the insertions due to missing data and the propensity score trimming process (Section 9.7.1.3.2)—the number of first insertions of an IUD available through June 2018 from the four health care systems is anticipated to be approximately 225,000, with breastfeeding status available for approximately 60,000. For the two primary objectives related to the risk of uterine perforation, the power of the study is calculated for differences in the estimated risk of uterine perforation with respect to (1) breastfeeding status at the time of IUD insertion and (2) time interval of the IUD insertion following delivery. The null hypothesis to be tested for primary objective 1 is that the natural logarithm of the adjusted summary perforation hazard ratio for breastfeeding versus not breastfeeding at the time of IUD insertion is equal to 0. Using information from validation study, the expected allocation ratio of breastfeeding versus not breastfeeding is 60:40 for this objective. Three null hypotheses to be tested for primary objective 2 are that the natural logarithm of the adjusted summary perforation hazard ratio for early (i.e., ≤ 6 weeks postpartum, > 6 and ≤ 14 weeks, > 14 and < 52 weeks) versus later (i.e., > 52 weeks) postpartum IUD insertion is equal to 0. Based on information from the validation study, the expected allocation ratio of the corresponding postpartum period categories is 5:20:5:70 for this objective.

Power calculations for the expected number of IUD insertions were performed using PASS 14 software (NCSS, LLC, Kaysville, Utah) for a two-sided test of the hazard ratio (Schoenfeld, 1983). Table 4 indicates the power to detect various hazard ratios at the two-sided $\alpha = 0.05$ significance

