level based on a perforation risk of 1.3 per 1,000 insertions and the percentage of insertions expected for the exposure groups of interest, i.e., breastfeeding versus not breastfeeding and early versus late postpartum insertion for the two cutpoints of interest.

Table 4. Power to detect hazard ratio for uterine perforation based on anticipated number of intrauterine device insertions and exposure group allocation

Exposure groups	Number of insertions expected	Allocation % (exposed: unexposed)	Hazard ratio that can be detected (% power)				
			1.5	1.75	2.0	2.25	2.5
Primary objective, 1: Breastfeeding vs. not breastfeeding	60,000	60:40	42	68	85	94	98
Primary objective, 2: Categories of postpartum insertion timing: ≤ 6 weeks vs. > 52 weeks, including women without a recorded delivery within the past 52 weeks	168,750	5:70	32	54	73	85	92
Primary objective, 2: Categories of postpartum insertion timing: > 6 and ≤ 14 weeks vs. > 52 weeks, including women without a recorded delivery within the past 52 weeks	202,500	20:70	78	97	> 99	> 99	> 99
Primary objective, 2: Categories of postpartum insertion timing: > 14 weeks and ≤ 52 weeks vs. > 52 weeks, including women without a recorded delivery within the past 52 weeks	168,750	5:70	32	54	73	85	92

Table 5 displays the power to detect various hazard ratios at the two-sided $\alpha = 0.05$ significance level for the risk of perforation among LNG-releasing versus copper IUDs based on a perforation risk of 1.3 per 1,000 insertions and the percentage of insertions expected for the exposure groups of interest, i.e., timing of postpartum insertion and breastfeeding versus not breastfeeding.*

* These numbers are provided per the FDA request in the letter of 18 May 2016 to address the request to account for “sufficient number of users of both types of IUDs to allow secondary analyses of the comparative safety of LNG IUSs vs. copper IUDs with regard to early postpartum insertion and breastfeeding status at the time of insertion.” These power calculations are not necessarily directly linked to objectives, but rather indicate that adequate data are likely to be available to characterize comparative safety of LNG IUSs and copper IUDs.

Table 5. Power to detect hazard ratio for uterine perforation for LNG versus copper IUDs based on anticipated number of intrauterine device insertions and an 80% (LNG) versus 20% (copper) exposure group allocation

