Two-sided 95% CIs of the adjusted hazard ratios for uterine perforation will be presented overall or by data source, as appropriate. If the exposure-by-data source interaction is not significant, then the corresponding two-sided test of the null hypothesis that the natural logarithm of the overall adjusted hazard ratio equals 0 will be performed. The significance level of 0.05 will be applied. There will be no adjustment for multiplicity.

As a sensitivity analysis, confounding effects will be accounted for by including selected key covariates in the unweighted Cox models. The Cox models will include exposure, site, exposure-by-site interaction, and baseline covariates. Due to the sparse outcomes, limited covariates will be selected for inclusion based on their association with the study outcome. The sensitivity analysis will be conducted only for the primary objectives.

Planned Analysis Tables 1.1 (for breastfeeding status) and 2.1 (for postpartum status) will present crude hazard ratio and hazard ratio adjusted via overlap weighting. Analysis Tables 1.2.1 through 1.3.5 and 2.2.1 through 2.3.5 will present baseline characteristics by exposure and standardized differences (described in Section 4.1.5) prior to and after overlap weighting. Analysis Tables 1.4 and 2.4 will present hazard ratios adjusted by including baseline covariates in the model. Results related to the development of propensity score models will be presented in Analysis Tables 33.1.1, 33.2.1, 33.2.2, 33.3.1, 33.3.2 and Analysis Figures 33.1.1 and 33.1.2.

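### If the proportional hazards check fails, the primary hazard ratio model gains a time term whose form is chosen from the outcome curves, and the plan does not say which P value then decides the primary objectives

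*SAP*

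**What the plan says.** SAP 4.1.4 checks proportional hazards for each exposure-outcome pairing with plots and a global Schoenfeld-residual test at 0.05. If both point to non-proportionality, an interaction of exposure with continuous or categorical time enters the crude and adjusted models, and separate hazard ratios over time are reported. The timing of the choice is explicit: "The form of the interaction terms will be determined after reviewing the plots of hazard functions and log-log survival curves". The half-year split in the sample code is marked as an example only.

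SAP 4.1.6 carries this into the weighted model that serves the primary objectives: "Time-dependent exposure covariates will be included if violation of the proportional hazards assumption is identified in the unweighted Cox model". Programming note 2 to Table Layout 2.1 (objective 1) then expands the primary table with separate hazard ratios over time. Table Layout 2.2 (objective 2) has no such note, although 4.1.4 applies there too.

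SAP 6.2.1 defines the primary test. If the exposure-by-data-source interaction is not significant, "the corresponding two-sided test of the null hypothesis that the natural logarithm of the overall adjusted hazard ratio equals 0 will be performed". That is the only condition it states. Protocol 4.9 sets "two-sided statistical tests with a significance level of 0.05" for both primary objectives, Protocol 9.7.3.1 rejects the null at P ≤ 0.05, and SAP 6.2.1 adds "There will be no adjustment for multiplicity". Protocol 9.7.1.3.1 leaves the details of the time terms to the SAP.

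**The concern.** Once an exposure-by-time term is in the model, no coefficient is the overall log hazard ratio. With the SAP's sample code, the main effect is the log hazard ratio up to the cut, and the later period needs a sum of two coefficients. With continuous time, the main effect refers to time zero on whatever scale is used. Neither is the quantity named in SAP 6.2.1, and no section says which coefficient, contrast or joint test takes its place.

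The time function is also settled after the analysts have seen the curves for the same outcome. A split placed where the curves differ most tends to make one period look significant even when exposure has no effect. At stake is the formal conclusion on both primary objectives of a postmarketing requirement: two analysts could follow the plan faithfully and report different primary P values.

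**Working it through.** **Inputs.** Protocol 9.5 and Table 4: power "level based on a perforation risk of 1.3 per 1,000 insertions"; first insertions "approximately 225,000, with breastfeeding status available for approximately 60,000"; for objective 1, "the expected allocation ratio of breastfeeding versus not breastfeeding is 60:40 for this objective"; for objective 2, a 5:20:5:70 split. Two-sided alpha is 0.05, and the proportional hazards test is at 0.05 (SAP 4.1.4).

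**The plan's own figure.** Objective 1 events: 60,000 × 0.0013 = 78. Schoenfeld power at a hazard ratio of 2.0 is Φ(√(78 × 0.6 × 0.4) × ln 2 − 1.96) = Φ(4.327 × 0.693 − 1.96) = Φ(1.04) = 85.1%, against the stated 85%. The rest of the Table 4 row reproduces as well (41.9, 67.8, 93.9 and 97.7%).

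**Assumptions not in the plan.** (a) The branch opens on the test alone. (b) Any period with P < 0.05 counts as a finding. (c) Time is split into two periods, with the cut after 20% to 80% of events, because the timing of events is not given. (d) Exposure has no effect at any time.

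**Formula.** Overall rate = P(branch) × rate inside the branch + P(no branch) × rate of the single-HR test there. Under the null, P(branch) is about 0.05 and the last rate is about 0.049.

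**Objective 1, simulation with 78 events and a 60:40 split.** Ranges cover an event-rank or a skewed time scale for the proportional hazards test, except in the five-cut row, which uses event rank.

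| Rule inside the branch | Rate given branch | Rate over all studies |
|---|---|---|
| Single-HR test kept | about 5% | about 5.0% |
| Fixed cut | 25% to 49% | 5.9% to 7.1% |
| Best of 3 cuts | 56% to 70% | 7.4% to 8.1% |
| Best of 5 cuts | 79% to 82% | 8.6% to 8.7% |
| Exhaustive search | 94% to 99% | 9.2% to 9.6% |

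Arithmetic check, fixed middle cut: 0.0496 × 0.485 + 0.9504 × 0.049 = 0.024 + 0.047 = 7.1%. Best of three cuts: 0.0496 × 0.699 + 0.047 = 0.035 + 0.047 = 8.1%. Ceiling, if the branch always gave a false positive: 0.05 × 1 + 0.95 × 0.05 = 9.75%.

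**Objective 2.** 225,000 × 0.0013 = 292.5 events, simulated as 292 with the four-group split and a 3-df global test. The chance of at least one false positive among the three comparisons goes from 14.0% to 16.9% with a fixed middle cut. With the best of five cuts it goes from 13.8% to 17.1%, and the per-comparison rates are 6.0%, 6.9% and 6.0% against 4.7%, 5.3% and 4.6%.

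**Power cost of splitting.** At a constant hazard ratio of 2.0, an even split leaves 39 events per period: Φ(√(39 × 0.24) × 0.693 − 1.96) = Φ(0.16) = 56% per period, against 85% for the single test.

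**The case against.** The plan does not say that a significant period rejects the primary null; it says only that separate hazard ratios are reported. SAP 6.2.1 still asks for the overall test, and Table Layout 2.1 is expanded rather than replaced, so the period results can be read as additions. That is fair, and it is why the rates above are conditional on an assumed rule. It does not settle the matter, because SAP 4.1.4 and 4.1.6 put the time term into the adjusted model itself, and the overall hazard ratio cannot be read from that model.

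A reader might infer that the rule nearly doubles the false-positive rate. The documents do not support that. A figure near 9.75% needs an exhaustive search for the cut, or two periods that are always tested; continuous time, also allowed, has no cut. The required visual agreement can only make the branch rarer. For objective 2 the inflation is about 1.2-fold (16.9/14.0).

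A reader might also infer that the check is likely to fail, because Protocol 9.7.1.2.1 expects the risk to change over time. That concerns the underlying hazard, which Cox regression leaves free. Proportionality concerns the ratio, and the documents give no basis for a probability of failure.

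Protocol 9.9 declines multiplicity adjustment so as not to miss a harm. That reasoning covers the planned comparisons. It does not address a time split chosen from the outcome, and splitting itself costs power.

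**Conclusion.** The point holds as a defect in the definition of the primary analysis. In the non-proportional branch the primary P value is undefined, and the form of the model is chosen from the outcome curves. This follows from the text alone.

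The size is moderate over the whole procedure and large inside the branch. If any significant period is read as a difference, the objective 1 rate is about 6% to 7% with a fixed cut and about 7% to 9% with a cut chosen among a few candidates, instead of 5%. Given entry on the test alone, it is roughly 25% to 50% and 55% to 85% respectively. For objective 2, the chance of any false positive rises from about 14% to 17%. The overall figures lie on the upper side because the visual condition is left out.

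They rest on no effect at any time, unweighted residuals, one-year event counts and assumed event timing; a run with 200 events gave similar rates. If hazards truly are non-proportional, that null is false and the error rates do not apply, but the undefined P value remains. That the period results replace the primary test outright is an inference the text does not settle; the sections have to be reconciled.

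**What to change.** State in SAP 4.1.4, 4.1.6 and 6.2.1 that the weighted hazard ratio from the model without a time term, with robust standard error, supplies the primary estimate and P value whatever the proportional hazards check shows. If proportionality is doubtful, add period-specific hazard ratios as descriptive results, without a decision rule, at a cut fixed now. One year is a natural example, since objectives 17 and 25 and the cumulative incidence tables already use it, although that horizon was not chosen because the effect is expected to change there. Carry the same wording into the notes to Table Layouts 2.1 and 2.2.

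This keeps the objective 1 level at about 5% and takes a few sentences. The cost is that under non-proportional hazards the single hazard ratio is an average that depends on the length of follow-up; the descriptive period results disclose this. A 2-df joint test at a pre-specified cut would also hold the level at about 5%, if the team prefers a test that allows for a changing effect.
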